12.1.1 Version 2 SF-36 survey

The version 2 SF-36 health survey, standard (4-week) recall form will be adopted for general QOL measure in this study. This widely used, generic instrument derives eight scales (physical functioning, role-physical, bodily pain, general health, vitality, social functioning, role-emotional, mental health) and two summary components (physical and mental). For these analyses we will use only the physical and mental composite scales.

12.1.2 European Quality of Life Questionnaire

The EQ-5D is a public domain instrument. This instrument is a utility measure that generates a descriptive profile and single index value for health status. The descriptive portion addresses five health dimensions (mobility, self-care, usual activities, pain/discomfort, and anxiety/depression). The second portion of the EQ-5D is a (0-100) visual analogue scale that is used to report overall health status.

12.2 *Disease-Target Measures*

12.2.1 Diabetes Distress Scale

The DDS represents the latest iteration of the Problem Areas in Diabetes (PAID) scale. This is a 17-item self-administered questionnaire selected from a longer battery of 28-items.

12.2.2 Hypoglycemia Fear Scale

The HFS is a 23-item self-administered survey for measuring the fear experienced with respect to hypoglycemia. The HFS has two subscales. The first measures hypoglycemia avoidance behavior, and the second measures worry about hypoglycemia.

12.3 *Statistical Analyses of Quality of Life Measures*

We will analyze QOL data at each time point independently. Separate univariate analyses will be performed for each scale and for the change from baseline for each scale. Since all QOL measures are at least ordinal scale, we will use the methods described for continuous outcomes. We will also perform a longitudinal analyses for the composite scores for QOL measure.

Each analysis will display mean, standard deviation, median, minimum, and maximum for the outcome. A 95% confidence for the scale and for the change from baseline for that scale will be computed using the method described for continuous outcome measures.

12.3.1 Analysis for SF-36 survey

Separate analyses for the SPC and SMC scales for each time point. Each composite score and their change from baseline values will be analyzed using the methods described for continuous variables.

In addition, we will perform the following longitudinal analyses. For each subject, we will include his/her score at baseline, 75±5, 365±14 days, 730±14 days, and 1095 ±14 days following the last islet transplant. We will use the linear mixed models with a term for time (baseline, 75 days, 365, 730, and 1095 days following the last islet transplant) and repeated measures on subjects.

The Shapiro-Wilk test is applied to test the hypothesis that the QOL scores are normally distributed. If the normality hypothesis is not rejected at significance level 0.05, a linear mixed model analysis will be performed using the observed test scores to test whether the mean QOL score is the same among the five time points. The results would be treated as follows:

- If the p-value for time is greater than 0.05, we conclude that there is no evidence to claim that QOL is changing over time.
- If the p-value is less than 0.05, we would compute the overall 95% confidence intervals for the pair-wise differences in the QOL score.

If the normality hypothesis is rejected at significance level 0.05, we will use the bootstrap procedure (sampling subjects with replacement) to construct the overall 95% confidence intervals for the pair-wise difference in the QOL score between any two time points. We will use the Benjamini and Hochberg (Benjamini & Hochberg, 1995) adjustment for multiple tests.

12.3.2 Analysis for European Quality of Life Questionnaire

Separate analyses of Overall Health Status (OHS) score from the EQ-5D will be computed for 75±5 days after each transplant (unless a subsequent transplant has occurred), at one year, 2 years, and 3 years after the first and last transplants. We will calculate the sample mean and construct the 95% confidence interval of the mean OHS using the method for a continuous variable described above.

Statistical Analysis Plan

The longitudinal analysis will be repeated for the OHS.

12.3.3 Analysis for Diabetes Distress Scale

Separate analyses of DDS will be computed for 75 ± 5 days after each transplant, and at one year, 2 years, and 3 years after the first and after the last islet transplants. We will calculate the sample mean and construct the 95% confidence interval of the mean DDS using the method for a continuous variable.

The longitudinal analyses will be repeated for the DDS.

12.3.4 Analysis for Hypoglycemia Fear Scale

Separate analyses of HFS will be computed for 75 ± 5 days after each transplant, and at one year, 2 years, and 3 years after the first and last transplants. We will calculate the sample mean and construct the 95% confidence interval of the mean DDS using the method for a continuous variable described in SAP section 9.2.2.

The longitudinal analyses will be repeated for the HFS.

12.4 *Analysis of Secondary Time to Event Outcomes*

Time to event outcomes include the following:

- Time to death (all cause and also cardiac related) and time to cardiovascular events (death, CVA, MI)
- Time to $HbA1c \leq 6.5\%$
- Time to first severe hypoglycemia episode
- Time to $HbA1c$ decreasing by at least 1%
- global treatment failure composite outcome measure defined as the time to the first occurrence of any of the following:
 - Death
 - Stroke
 - MI
 - Above the ankle amputation

All of the above will be ascertained from the SAE reports and will be adjudicated if an adjudication committee is available.

- Renal Failure (Any one of the following):
 - Initiation of dialysis; or
 - Renal transplantation
- Blindness: Visual acuity of 20/200 in both eyes.

Statistical Analysis Plan

- Poor diabetes control (if any of the following occur):
 - HbA1c > 9% and reduced less than 1% below the entry level, found 6 months or more following the first transplant and confirmed on repeat examination at least 30 days and no more than 60 days later. If confirmed, failure is the time of the initial draw;
 - Three consecutive monthly HbA1c values greater than the baseline value, with the first one being 6 months or more following the first transplant; or
 - Occurrence of two severe hypoglycemic events (requiring assistance from another person) within a three month period. Failure will occur at the time of the second hypoglycemic event.

The endpoints and the analyses in this protocol have adopted two principal time points for each transplanted subject: (1) the time of the first transplant and (2) the time of the last transplant. It is of interest to examine the time to events following each of these time points. The following analyses will be repeated using each of these milestones as time zero in the analysis. In the unlikely event that a subject has already reached an event at the time of the second transplant he/she will not be included in the analyses for that event for time from last transplant.

All time to event outcomes will be summarized using Kaplan-Meier life table methods and survival plots. Estimates and 95% confidence intervals will be provided for rates at 1-year, 2-years, and three years after the first and after the last islet transplant. Confidence intervals will be computed as the estimate ± 1.96 standard errors of the product-limit estimates.

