In this study, five QOL measures are considered. Two scales are obtained from the SF36 questionnaire (version 2). These scales are the Summary Physical Component score (SPC) and the Summary Mental Component score (SMC). Additional QOL assessments include the Overall Health Status (OHS) measure based on the European Quality of Life (EQ-5D) instrument, the Diabetes Distress Scale (DDS), and the Hypoglycemia Fear Scale (HFS) scales.

The SF36 scales will be standardized to the US population. The EQ-5D OHS questionnaire provides two sub-scales: the Behavior subscale that is based on 10 questions and ranges from 0 to 40 and the Worry subscale that is based on 13 questions. The scale is computed as the sum of the responses to the 13 questions and ranges from 0 to 52. The DDS is based on 17 questions rated on a 6 point Likert scales and ranges from 17 to 102. The HFS has two subscales: the Behavior scale which ranges from 0 to 40 and the Worry scale that ranges from 0 to 52.

2.6 *Time to Event Outcomes*

Multiple time-to-event outcomes will also be studied. All events will be defined for the period from the first transplant to 1095 days after the last islet transplant.

- Time to death (all cause and also cardiac related) and time to cardiovascular events (death, CVA, MI)
- Time to $HbA1c \leq 6.5\%$
- Time to first severe hypoglycemia episode
- Time to $HbA1c$ decreasing by at least 1%
- Time to global treatment failure composite outcome measure defined as the time to the first occurrence of any of the following:
 - Death
 - Stroke
 - MI
 - Above the ankle amputation

All of the above will be ascertained from the SAE reports and will be adjudicated if an adjudication committee is available.

- Renal Failure (Any one of the following):
 - Initiation of dialysis; or
 - Renal transplantation
- Blindness: Visual acuity of 20/200 in both eyes.
- Poor diabetes control (if any of the following occur):
 - $HbA1c > 9\%$ and reduced less than 1% below the entry level, found 6 months or more following the first transplant and confirmed on repeat examination at least

Statistical Analysis Plan

30 days and no more than 60 days later. If confirmed, failure is the time of the initial draw;

- Three consecutive monthly HbA1c values greater than the baseline value, with the first one being 6 months or more following the first transplant; or

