2.7 Safety endpoints

Safety endpoints include the following:

At 75 ± 5 days following each transplant, at 365 ± 14 days following the first and last islet transplant(s), at 730 ± 14 days following the last islet transplant, and at 1095 ± 14 days following the last islet transplant:

- The incidence and severity of adverse events (AEs) related to the islet transplant procedure, including: bleeding (>2 g/dL decrease in hemoglobin concentration); segmental portal vein thrombosis; biliary puncture; wound complication (infection or subsequent hernia); and increased transaminase levels >5 times upper limit of normal (ULN)
- The incidence and severity of AEs related to the immunosuppression including: allergy; reduction in glomerular filtration rate (GFR); increase in urinary albumin excretion; addition or intensification of anti-hypertensive therapy; addition or intensification of anti-hyperlipidemic therapy; oral ulcers; lower extremity edema; gastrointestinal toxicity; neutropenia, anemia, or thrombocytopenia; viral, bacterial, or fungal infections; and benign or malignant neoplasms
- The incidence of change in the immunosuppression drug regimen
- The incidence of immune sensitization defined by presence of anti-HLA (histocompatibility antigen) antibodies absent prior to transplantation
- The proportion of subjects who withdraw from study treatment due to an organ transplant

At 365 ± 14 days following the first and last islet transplant and at 1095 days following the last islet transplant:

- The incidence of worsening retinopathy as assessed by change in retinal photography

3. Subgroup Analysis

A Subject may enter the study because she/he is having severe hypoglycemic events that require assistance or because she/he is unable to reduce HbA1c level to below 7.5% on Intensive Insulin

Statistical Analysis Plan

Therapy (see inclusion criterion 7 in the protocol). The latter group may be very small. However, if there are at least 6 subjects in each group, we will perform subgroup analyses that examine these two subgroups separately. Analyses will include all primary and secondary outcome measures and use the same analysis strategies that were used for those measures. Please note that power for these analyses will be very small but the results may lead to a better understanding of the mechanisms of outcome.

4. Sample Size and Power Calculations

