Table 3.3 summarizes data provided by clinician investigators in Europe and North America. GRAGIL, CITR, and the Nordic Group reported data for HbA1c levels at one year after first transplant but did not report data on hypoglycemic events. Rates for $HbA1c \leq 6.5\%$ varied from 50% to 83.3%. Overall, 70% (33 of 47) of islet transplanted patients from the three studies reporting 12 month HbA1c values would have satisfied the HbA1c requirement for a favorable outcome one year after their first islet transplant (95% confidence interval 57% to 83%). These rates do not include those whose HbA1c levels decreases by 1% or more at one year but did not reach 6.5%. While these reports do not give the incidence of hypoglycemia in these patients, the Edmonton group has reported that the incidence of hypoglycemic events in those with a successful islet transplant is very low. The lower portion of Table 3.3 provides HbA1c data on potentially eligible subjects identified during preliminary screening at several CIT clinics. Note that the baseline HbA1c levels are similar to those from the studies that present outcome data. These data argue that we can expect to observe favorable outcome rates that are not lower than those observed by the three groups.

We expect to observe a success rate greater than 55%. The proposed IAK study has approximately 90% power to detect this difference.

Statistical Analysis Plan

Table 4.3: HbA1c levels and favorable outcomes reported by investigators in Europe and North America

Reporting Group	Occasion	Number of transplanted subjects	HbA1c % (mean±sd)	HbA1c ≤ 6.5 one year after first transplant
GRAGIL	Pre transplant	8	7.7±0.6	50% (3/6) ¹
CITR ²	Pre transplant	12	NR ³	83.3% (10/12)
Nordic Group ²	Pre transplant	29	9.0±1.7	69.0% (20/29)
	Post transplant	29	7.4±1.5	
Maffi	Pre transplant	54	8.1±1.6	NR
	Post transplant	46	7.5±1.2	
Giessen ⁴	Pre transplant	21	8.7±0.4	NR
	Post transplant	21	7.1±0.3	
HbA1c levels reported by CIT Investigators				
Edmonton	Pre transplant	8	9.3±2.0	
Pennsylvania	Pre transplant	38	8.6±1.7	
Northwestern	Pre transplant	9	6.9±1.6	
Miami, Pennsylvania, and Northwestern	Change pre transplant to 12-months post transplant	16	-1.5±1.8	

¹ HbA1c < 6.5% but hypoglycemia events not reported

² The CITR has data on 17 IAK patients who are at least one year post first transplant.

³ NR=not reported

⁴ Both IAK and SIK reported

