12.5 Sensitivity Analysis

Measurements of secondary endpoints may be missing at any time point. In our analysis report for the secondary endpoints, we will not impute missing values in the analysis but will report results for the observed data only. With close monitoring and data validation, the chance of having missing values will be minimized except that some serious adverse events (SAEs) may force subjects to withdraw from the study treatment or withdraw consent without a particular reason during the study. The interpretation of our analysis is strictly applied to the efficacy measurable population. However, a sensitivity analysis will be performed to determine the potential effect that missing values have on the analyses of the secondary endpoints.

Missing values due to SAE will be excluded from this analysis. The analysis on these subjects will be provided in SAP section 14.

We will conduct a sensitivity analysis assuming a missing at random mechanism: *i.e.*, we assume that a subject will withdraw consent at random with probability r . This probability will be estimated at each time point.

We will use the method of multiple imputation (Schafer, 1999) to develop estimates and standard errors that account for the missing data. We will compare the magnitude of the differences between multiple imputation estimates and observed data estimates to assess the potential affect

Statistical Analysis Plan

of the missing data. The assumption of missing at random cannot be verified and these results must be viewed with caution.

13. Other Exploratory Analyses

13.1 *Change from baseline*

For each secondary outcome and time point where it is appropriate, we will explore the change from baseline over time. The endpoints and time points are as follows:

- insulin requirements (measured quarterly years 1 and 2 post-first and post-last transplant then every 6 months until year 3 post-last transplant)
- HbA1c (measured at day 28 and then quarterly years 1, 2, and 3 post-first and post-last transplant)
- Clarke Score (measured at 6 months and year 1 post-first and post-last transplant then every 6 months until year 3 post-last transplant)
- β score (measured quarterly year 1 post-first transplant, quarterly years 1 and 2 post-last transplant then every 6 months until year 3 post-last transplant)
- Basal glucose (measured quarterly year 1 post-first transplant, quarterly years 1, 2, and 3 post-last transplant)

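### Section 12.4 gives no at-risk rule for time to HbA1c ≤6.5% from the first transplant, so subjects already at target can be scored as early successes

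*SAP*

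**What the plan says.** SAP sections 2.6 and 12.4 list time to HbA1c ≤6.5% among the time-to-event outcomes and put no condition on the pre-transplant value. Section 2.6 sets the period: "All events will be defined for the period from the first transplant to 1095 days after the last islet transplant". Section 12.4 adds the estimator, "All time to event outcomes will be summarized using Kaplan-Meier life table methods and survival plots", with rates at 1, 2 and 3 years after the first and after the last transplant.

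Section 12.4 has the only at-risk rule. If a subject "has already reached an event at the time of the second transplant he/she will not be included in the analyses for that event", this applies to time from the last transplant. Sections 2.6, 8.3 and 12.4 have no counterpart for time from the first transplant.

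On who may enter, section 3 describes two routes: a subject enters because "she/he is having severe hypoglycemic events that require assistance or because she/he is unable to reduce HbA1c level to below 7.5"%. Of the second route it says "The latter group may be very small".

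Section 13.1 gives the measurement schedule as "HbA1c (measured at day 28 and then quarterly years 1, 2, and 3 post-first and post-last transplant".

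**The concern.** A subject who is already at the target cannot newly reach it. The authors saw this problem, since they remove such subjects on one clock, but they left the other clock open.

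The existing rule is also keyed to a second transplant. A subject at target before treatment who receives only one transplant has the same time zero on both clocks and is removed from neither. One who receives two transplants, and whose HbA1c is found at target in between, can count as an early success on the first clock and be absent from the second.

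The section 3 entry routes make such subjects plausible. The SAP states no HbA1c floor for the hypoglycemia route, and it expects few subjects by the other one.

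At stake is the reading of one curve and its 1-, 2- and 3-year rates. Successes present before treatment raise the curve and shorten the apparent time to response. The error cannot go the other way.

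**Working it through.** **The plan's own attainment figure.** Section 4 pools three series with HbA1c ≤6.5% one year after first transplant: 3/6 + 10/12 + 20/29 = 33/47 = 70.2%. The interval is ±1.96 × √(0.702 × 0.298/47) = ±13.1 points, so 57% to 83%. Both match the SAP. The SAP gives no figure for the share at or below 6.5% before transplant.

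**Share already at target (q).** Table 4.3 gives only means and SDs, so a distribution must be assumed. Under normality, q = Φ((6.5 − mean)/SD):

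| Pre-transplant row of Table 4.3 | n | Share ≤6.5% |
|---|---|---|
| CIT screening, 9.3±2.0 | 8 | 8.1% |
| CIT screening, 8.6±1.7 | 38 | 10.8% |
| CIT screening, 6.9±1.6 | 9 | 40.1% |
| Reported series, 7.7±0.6 | 8 | 2.3% |
| Reported series, 9.0±1.7 | 29 | 7.1% |
| Reported series, 8.1±1.6 | 54 | 15.9% |
| Reported series, 8.7±0.4 | 21 | 0.0% |

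Weighted by n:

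- Three CIT screening rows (n=55): (8 × 0.081 + 38 × 0.108 + 9 × 0.401)/55 = 15.2%.
- The same without the 9-subject row (n=46): (8 × 0.081 + 38 × 0.108)/46 = about 10%.
- Four reported series (n=112): 9.6%.
- All seven rows (n=167): 11.5%.

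A lognormal shape gives about 14% for the CIT rows and 10 to 11% for all seven. A working range is therefore 10 to 15%: 24 × 0.10 = 2.4 and 24 × 0.15 = 3.6, about 2 to 4 subjects. The lower limit is zero: section 4 selects the historical comparison group by an average HbA1c above 7.0%, and if that held for every transplanted subject, nobody would start at target.

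**Excess in the reported rate.** Let t be the true cumulative attainment among subjects who start above 6.5%. Ignoring censoring, and if every subject in q is scored as an event, the reported rate is q + (1 − q)t. The excess over t is q(1 − t).

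| t | q = 0 | q = 10% | q = 15% |
|---|---|---|---|
| 70% (section 4) | 0 | 3.0 points | 4.5 points |
| 50% (assumed) | 0 | 5.0 points | 7.5 points |

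The 70% may itself include subjects who began at target. In that case t = (0.70 − q)/(1 − q), and the excess is q × 0.30/(1 − q): 0.030/0.90 = 3.3 points and 0.045/0.85 = 5.3 points. The range is nearly the same.

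**Against sampling error.** With 24 subjects and no censoring, the standard error is √(0.7 × 0.3/24) = 9.4 points at 70% and √(0.5 × 0.5/24) = 10.2 points at 50%. The excess is about a third to a half of a standard error in the first case and a half to three quarters in the second.

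**The case against.** Four points can be made on the other side.

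- **Eligibility is set in the protocol.** Section 2.2.1 refers to it, and it may contain an HbA1c floor. Section 4's >7.0% assumption points that way, and the CIT rows describe potentially eligible subjects at preliminary screening, before up to 12 months of intensive insulin therapy. This stands as a limit on size: the share is unknown and may be zero. It does not remove the gap, because the >7.0% figure is an assumption for selecting historical controls and section 3 describes a different entry route.
- **The curve may be meant to show being at target, whatever the baseline.** The primary endpoint and the corresponding key secondary endpoint count HbA1c ≤6.5% that way. That would be a coherent choice, but section 12.4 treats subjects already at the event as not at risk on the other clock. The mismatch remains.
- **Baseline-relative response is covered elsewhere.** The SAP also analyses time to a 1% fall, the proportion with a 1-point fall, and change from baseline, and it tabulates baseline HbA1c. This is true and lowers the stakes. It does not correct this curve.
- **The outcome is descriptive.** Section 10.2 says secondary outcomes are not to be used explicitly for the efficacy decision. This stands.

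A reader might also infer that Table 4.3 shows about 16% already at target. It states no such share. A figure near 16% needs a normal shape plus either a single row (n=54) or a cut-off moved to 6.55 in the CIT rows, whose average is pulled up by nine subjects.

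Nor does the SAP say that these subjects become events at the day 28 draw. That requires the day 28 value also to be ≤6.5%, or baseline to count at time zero. The SAP fixes neither, and the day 28 schedule comes from an exploratory section.

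**Conclusion.** The gap is real and limited. Section 12.4 applies an at-risk rule to one clock and not to the other, so time to HbA1c ≤6.5% from the first transplant can be biased, and only upward.

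Assuming normality in Table 4.3, roughly 10 to 15% of subjects are affected, about 2 to 4 of 24, and possibly none. The excess is about 3 to 5 points at 70% attainment, about 5 to 8 points at an assumed 50%, and zero if nobody starts at target. These figures assume no censoring and that every subject at target before transplant is scored as an event.

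A reader might take this to mean that the trial's efficacy result is inflated. The SAP does not support that: the primary exact binomial test, its 27% null rate, the sample size and the multiplicity adjustment of the key secondary endpoints do not use this curve.

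**What to change.** In section 12.4, state that time to HbA1c ≤6.5% from the first transplant includes only subjects whose last pre-transplant HbA1c is above 6.5%. Apply the same condition to time from the last transplant for subjects who have only one transplant. Report the number already at target beside the curve.

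This costs one sentence in the SAP and, if the shares above hold, about 2 to 4 fewer subjects at risk in this curve. If the protocol already excludes such subjects, the sentence changes nothing.

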8.2 Analysis of binary outcome variables

Binary outcome variables will be displayed as percents with 95% exact confidence intervals (Rosner, 1995). The exact confidence interval (P_L, P_U) will be as the solutions to the following equations. If x is the observed outcome (that is, there are x successes in the 24 subjects) then the lower bound will be the solution P_L to the equation

$$0.025 = \Pr \{ \text{at least } x \text{ successes} \mid \text{probability of success} = p_L \} = \sum_{k=x}^{24} \binom{24}{k} p_L^k (1-p_L)^{24-k}.$$

The upper bound will be the solution to the equation

$$0.025 = \Pr \{ \text{no more than } x \text{ successes} \mid \text{probability of success} = p_U \} = \sum_{k=0}^x \binom{24}{x} p_U^k (1 - p_U)^{24-k}.$$

Standard search methods will be used to solve these equations.

8.3 *Analysis of time to event measures*

All time to event measures will be summarized using Kaplan-Meier (product limit) life table methods. Results will be displayed as survival plots. Tables with estimates and 95% confidence intervals for the rates at 1-year, 2-years, and 3-years after the first and last islet transplants will be provided. Separate analyses will be performed for time from first transplant and time from last transplant.

9. Analysis of Demographic and Baseline Measures

9.1 *Baseline Data*

Baseline data collected for the ITT analysis consists of demographic information and medical/physical assessments during the waiting period for islet transplant. These data will be grouped into the following categories:

- Demographic variables
 - Age
 - Sex
 - Race (White, Black, Hispanic, Asian and Other)
- Body Habitus and Quality of Life
 - Body Weight
 - Height
 - Body Mass Index (BMI)
- Diabetes Control
 - Insulin requirement (units/day)
 - HbA1c
 - Fasting and post prandial plasma glucose
 - Fasting and post prandial C-peptide
 - 90-minute C-peptide following consumption of Boost[®] or equivalent
 - 90-minute glucose following consumption of Boost[®] or equivalent
 - Number of severe hypoglycemic events in the last year
 - MAGE score
 - LI
 - Clarke Score
 - HYPO score
 - β -score
 - C-peptide/(glucose·creatinine) ratio

Statistical Analysis Plan

- Measures of Cardiovascular function
 - Carotid intimal thickness
 - Atherogenic profile (fasting lipids, c-reactive protein, serum amyloid A, Apolipoprotein A1, Apolipoprotein B, and the ratio of Apolipoprotein A1 and Apolipoprotein B).
- Measures of Renal function
 - Serum Creatinine

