The primary aim of the analysis is to estimate the true rate of favorable outcome at one year after their first transplant in all eligible subjects for whom induction for an islet transplant is begun. The observed favorable outcome rate and a one-sided 95% exact binomial confidence interval will be used to estimate the true favorable outcome rate. The primary analysis will compute a one-sided exact binomial test of the null hypothesis that the true rate is less than or equal to 27% versus the alternative that the true rate exceeds 27% (see sample size justification). The analysis will be considered to support efficacy if the null hypothesis is rejected at the 5% level of significance. The lower bound for the confidence interval p_L will be determined as the value that satisfies the following equation:

$$0.05 = \sum_{x \geq r} \binom{24}{x} p_L^x (1 - p_L)^{24-x}$$

The rates of favorable outcome and exact one-sided 95% confidence intervals will be computed for each contributing center.

Statistical Analysis Plan

This analysis will be conducted for the ITT population. The primary endpoint should be available for all treated subjects. An exception will be if a death occurs, if the subject withdraws consent to be followed, or if immunosuppression is begun but the subject never receives a transplant. In these cases the endpoint will be classified as failure to achieve a favorable outcome. Should the endpoint not be evaluated for a particular individual for other reasons, a failure will be imputed unless an evaluation is done at a time longer than one year after transplant, in which case, that later value will be imputed. All imputations will be reported with the primary analysis. The rates and the exact one-sided 95% confidence intervals for complete data and imputed data will be compared to ascertain the sensitivity of the imputation.

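### Kaplan-Meier is planned for events that death prevents (HbA1c attainment, first severe hypoglycemia, cardiac death); cumulative incidence should be reported instead

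*SAP*

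**What the plan says.** Section 8.3 of the SAP sets one method for the whole class: "All time to event measures will be summarized using Kaplan-Meier (product limit) life table methods". Section 12.4 repeats it: "All time to event outcomes will be summarized using Kaplan-Meier life table methods and survival plots". Rates with 95% confidence intervals are to be given at 1, 2 and 3 years after the first and after the last transplant. The intervals use 1.96 standard errors of the product-limit estimate.

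Sections 2.6 and 12.4 list the outcomes. Some count death as an event: all-cause death, cardiovascular events (which include death) and the global treatment failure composite. Others do not. These are time to HbA1c of 6.5% or below, time to HbA1c "decreasing by at least 1" percent, first severe hypoglycemia, and cardiac-related death, where only non-cardiac death lies outside the event. On follow-up, section 2.6 says: "All events will be defined for the period from the first transplant to 1095 days after the last islet transplant".

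The SAP names no competing-risk estimator and writes no censoring rule for death, withdrawal or loss to follow-up in these analyses.

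Section 12.5 reports secondary endpoints on observed data. It adds a multiple-imputation sensitivity analysis under missing at random, from which values missing because of a serious adverse event are left out.

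**The concern.** Kaplan-Meier treats a censored subject as still able to have the event, at the same rate as those who remain under observation. That is reasonable for someone whose follow-up simply stops. It is not reasonable for someone who has died, who cannot later reach an HbA1c target or have a hypoglycemic episode. Censoring that death removes the subject from the risk set and spreads his or her weight over the survivors, so the estimated event rate rises.

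At stake are the 1-, 2- and 3-year rates for four descriptive outcomes. For the two HbA1c outcomes the error flatters the treatment. For first severe hypoglycemia and cardiac death it makes the treatment look worse. With 24 subjects, a single death is enough to move a reported rate by a visible amount.

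**Working it through.** **Figures in the plan.** The SAP states no figure for these analyses and no death or dropout rate. Its only related calculation is for the primary endpoint, and it reproduces. With 24 subjects and a null rate of 27%, the exact one-sided 5% test rejects at 11 or more successes, with exact alpha 0.0369. Power is 0.9045 at 57% (stated as about 90%) and 0.7907 at 52% (stated as 80%). Nothing below alters those numbers.

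**Inputs for the illustration.** From section 4: n = 24. From section 13.1: HbA1c is measured at day 28 and then quarterly. Assumed, because the SAP is silent: 14 of 24 subjects reach the target, 6 at day 90, 4 at day 180, 2 at day 270 and 2 at day 365. Deaths among subjects who have not reached it fall just after the visit named.

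**Formulas.** With d events among n(t) at risk at visit t:

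- Kaplan-Meier with deaths censored: S(t) = product of (1 − d/n(t)); the reported rate is 1 − S.
- Aalen-Johansen: F = sum of [event-free survival just before t] × d/n(t), where event-free survival falls at deaths as well as at attainments.

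**One death after day 28.** Numbers at risk are 23, 17, 13 and 11.

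- S = 17/23 × 13/17 × 11/13 × 9/11 = 9/23 = 0.391, so 1 − S = 60.9%.
- F = (23/24)(6/23) + (17/24)(4/17) + (13/24)(2/13) + (11/24)(2/11) = 14/24 = 58.3%.

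With no other losses, the Aalen-Johansen estimate is simply the share of all 24 who attained the target. The same steps give:

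| Deaths before attainment (assumed timing) | 1 − Kaplan-Meier | Aalen-Johansen | Gap (points) |
|---|---|---|---|
| 0 | 58.3% | 58.3% | 0 |
| 1 (day 28) | 60.9% | 58.3% | 2.5 |
| 2 (day 28; day 90) | 63.0% | 58.3% | 4.7 |
| 2 (both day 28) | 63.6% | 58.3% | 5.3 |
| 3 (days 28, 90, 180) | 64.7% | 58.3% | 6.4 |
| 4 (two at day 28, then days 90 and 180) | 68.0% | 58.3% | 9.7 |

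**Timing matters.** If the 14 attain by day 270 and two non-attainers die at day 300, 1 − S is still 14/24 = 58.3% and the gap is zero. Only a death that is followed by further events creates a gap.

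**Three years.** Add 2 attainments at day 730 and 1 at day 1095, so that 17 of 24 (70.8%) attain. One death after day 90 gives 1 − S = 73.5%. Four deaths (after days 28, 90, 180 and 365) give 82.4%. The gaps are 2.7 and 11.5 points.

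**A check that does not rest on chosen visits.** Assume constant hazards, a Kaplan-Meier attainment of 57% at one year (borrowed from section 4 only as a convenient value) and a one-year death probability q. With a = −ln(1 − 0.57) and b = −ln(1 − q), cumulative incidence = a/(a + b) × (1 − exp(−(a + b))). For q = 2%, 5%, 10% and 20% this gives 56.5%, 55.8%, 54.5% and 51.9%, so the overstatement is 0.5, 1.2, 2.5 and 5.1 points.

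**Does section 12.5 repair this?** No. Death heads the list of serious adverse events in section 14.1, and section 12.5 leaves out values missing because of such events. The subjects who create the gap are therefore outside the check.

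**The case against.** The strongest reply is that these outcomes are descriptive. Section 10.2 says the secondary outcomes are not intended for deciding efficacy, the trial has 24 subjects, and there may be no death before attainment at all. The SAP also never writes that deaths will be censored; this is inferred from the method. All of that stands. It limits the importance of the point and makes its size conditional. It does not remove it, because a product-limit analysis with no other instruction has no other place to put a death.

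Three stronger readings are tempting and are not supported.

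- *That the plan contradicts its primary analysis.* Section 10.1 lists the cases, "An exception will be if a death occurs, if the subject withdraws consent to be followed", and rules: "In these cases the endpoint will be classified as failure to achieve a favorable outcome". That rule is for the primary endpoint, and section 10.2.1 extends it to the key secondary endpoints. The time-to-event outcomes are in neither group. Time to first attainment is also a different quantity from HbA1c status at day 365: a subject at target on day 90 and above it on day 365 counts in one and not in the other. The two sets of 1-year figures could differ with no deaths at all, and changing the estimator would not make them agree.
- *That withdrawals should be counted as non-attainment.* A subject who withdraws may still reach the target unobserved. Withdrawal is ordinary censoring and biases Kaplan-Meier only if it is informative. Section 12.5 does say that serious adverse events may force withdrawal, which is a reason for a sensitivity analysis but not for a change to the main estimate.
- *That the rates are certain to be overstated.* They are overstated only if a death precedes later events.

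**Conclusion.** The point holds in a limited form. For the two HbA1c outcomes, first severe hypoglycemia and cardiac-related death, Kaplan-Meier with competing deaths censored overstates the 1-, 2- and 3-year rates whenever a death precedes later events. The direction follows from the method. The size rests on assumed counts: at one year, about 2.5 points for one early death and up to about 10 points for four, with 14 of 24 attaining, and zero if no death precedes a later event. No planned analysis corrects it. The effect is confined to descriptive secondary summaries. The primary test, sample size and power stand.

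**What to change.** In sections 8.3 and 12.4:

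- Report Aalen-Johansen cumulative incidence, with its own standard errors in place of the product-limit ones, for time to HbA1c of 6.5% or below, time to a fall of at least 1%, and first severe hypoglycemia, with death as the competing event.
- Do the same for cardiac-related death, with non-cardiac death as the competing event.
- Keep Kaplan-Meier for all-cause death and for the composites that include death.
- Write down the censoring rules. Censor withdrawal of consent and loss to follow-up; scoring withdrawal as non-attainment should be at most a sensitivity analysis.
- Add a sentence noting that 1-year first attainment and the day-365 proportions in Table 10.1 measure different things and handle deaths and missing values under their own rules.

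The cost is a few sentences of SAP text and standard software. No data collection, sample size or primary analysis changes. If deaths precede later attainments, the reported HbA1c attainment rates will be somewhat lower.
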